## 2.2.Secondary objectives

- To evaluate the incidence in the cohort study.
- To evaluate the relation between the risk of infection and several factors (mobility, social characteristics).
- To evaluate individual immune dynamics (seroconversion, seroreversion).
- To compare the proportion of participants with positive test results between age (<20, 20-29, 30-39, 40-49, 50-59, 60-69, >70) and gender groups.

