## 3. Study procedures

### 3.1.Study design

This non-interventional observational socioepidemiological population study will be conducted in residents of St. Petersburg, Russia. Selection and invitation of participants will take place during telephonic survey. After giving signed informed consent, each participant will be subjected to a blood test for SARS-CoV-2 antibodies and will answer a questionnaire. The testing will be performed primarily using serological assays for serum IgG approved in the Russian Federation (Abbott Architect IgG and Genetico).

This study involves a telephonic sociological survey during which respondents will be invited to undergo a blood test for SARS-CoV-2 antibodies at the participating investigational sites in different cities and towns of Russia. The participants will undergo such a test, take part in an additional survey for those who plans or have already done such a test, and receive the results. A part of participants will be offered to use a taxi (see Section 5.2). Testing and questionnaire at the clinic will be repeated several times. It is planned to perform up to 10 visits which will include blood sampling, testing, and collection of additional information.

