#### **4. Laboratory diagnostics**

To measure IgG antibodies titer, Abbott Architect SARS-CoV-2 IgG (<https://www.fda.gov/media/137383/download>) assay will be used. According to the manufacturer, the sensitivity of the assay is 100%, and the specificity is 99.6%. With a scientific objective, Coronapass Total Ig assay (Genetico) will also be used, with the sensitivity of 96% and specificity of 100%, according to the manufacturer. Other point-of-care tests can be used to immediately inform participant but not for the research analysis.

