#### Cohort study:

- To evaluate the incidence (number of new cases of infection by number of participants and observation time, i.e. incidence rates per person-days). Participants with positive result at the first testing will not be included in this assessment.
- To evaluate the relation between different sociodemographic factors and incidence (rate ratios).
- To evaluate the dynamics of immune response:
  - cumulative seropositivity, i.e. proportion of positive tests at each moment;
  - cumulative seroconversion, i.e. cumulative proportion of participants at all moments with at least 1 positive test;
  - cumulative seroreversion, i.e. cumulative proportion of participants at all moments with at least 1 negative test after at least 1 positive test.

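### As defined, cumulative seroconversion is ever-seropositivity: it counts people already positive at the first visit, and seroreversion is divided by all participants instead of those ever positive

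*Protocol*

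**What the plan says.** Protocol Section 2.2 makes individual immune dynamics, meaning seroconversion and seroreversion, a secondary objective. Section 5.3.2 (cohort study) fixes how they are measured. The first measure is given as "cumulative seroconversion, i.e. cumulative proportion of participants at all moments with at least 1 positive test". The second, which needs two results in a set order, is given as "cumulative seroreversion, i.e. cumulative proportion of participants at all moments with at least 1 negative test after at least 1 positive test".

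Neither definition is limited to people who could have the event: those negative at entry for conversion, those already positive for reversion. Neither mentions confirming a result. The incidence item in the same list does restrict its population: "Participants with positive result at the first testing will not be included in this assessment". That sentence is attached to incidence only.

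On testing, Section 3.1 states: "It is planned to perform up to 10 visits which will include blood sampling, testing, and collection of additional information". Section 4 gives for the Abbott assay, in per cent, "According to the manufacturer, the sensitivity of the assay is 100%, and the specificity is 99.6", and for the Genetico assay it adds "with the sensitivity of 96% and specificity of 100%, according to the manufacturer".

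**The concern.** Seroconversion means passing from negative to positive. The definition asks only for one positive result at any time, so someone positive at every visit from the first is counted as a converter. Two measures in one list, both meant to describe new infection, then rest on different populations, and the one called seroconversion is mostly baseline prevalence when few new infections occur.

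Seroreversion has a different fault. Only a person who has been positive can revert, but the literal denominator is everyone. The result is the product of how many were infected and how many lost antibody, and cannot be read as antibody loss. Two cohorts with the same loss but different prevalence would report different values.

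Both measures also accept a single result out of as many as 10, so isolated test errors can add events. Section 6 says the data will be open for epidemic modelling, so a mislabelled measure could be carried into other work.

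**Working it through.** **Inputs.** Prevalence 10% (Section 5.1, second planning value); up to 10 tests (Section 3.1); Abbott sensitivity 100% and specificity 99.6%, Genetico 96% and 100% (Section 4); 1000 participants with 5% loss per repeat visit (Sections 3.1 and 5.1). The protocol gives no expected value for seroconversion or seroreversion. Its attrition figure reproduces: 1000 × 0.95^9 = 630.2, stated as 630.

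**Scenario.** No new infection and no antibody loss after entry, so a true conversion or reversion measure should read 0. The protocol does not say how errors behave between visits. I assume the two extremes: independent at each visit, or fully persistent within a person.

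**Seroconversion as defined, 10% prevalence**

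- Perfect test: 10.0%, all of it baseline positives.
- Abbott, persistent errors: 0.10 + 0.90 × 0.004 = 10.4%.
- Abbott, independent errors, 10 tests: 0.10 + 0.90 × (1 − 0.996^10) = 0.10 + 0.90 × 0.0393 = 13.5%.
- The same with planned attrition: the average of 1 − 0.996^k over the number of tests k actually taken is 3.16%, so 0.10 + 0.90 × 0.0316 = 12.8%.
- Genetico, independent errors, 10 tests: 10.0%, because its stated specificity is 100%.

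Baseline positives are thus 10 of the 13.5 points. At other, assumed prevalences, Abbott (persistent to independent, 10 tests) gives:

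| Prevalence | As defined |
|---|---|
| 2% | 2.4% to 5.9% |
| 5% | 5.4% to 8.7% |
| 14% | 14.3% to 17.4% |
| 20% | 20.3% to 23.1% |

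**Seroconversion restricted to participants negative at the first test**

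- Perfect test, or Abbott with persistent errors: 0%.
- Abbott, independent errors: 1 − 0.996^9 = 3.5% (2.8% with attrition).
- Also requiring two consecutive positives: about 8 × 0.004² = 0.01%.

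**Seroreversion.** For a person whose chance of a positive result at each test is q, the chance over k independent tests of a negative somewhere after a positive is 1 − Σ (1 − q)^a q^(k−a), summed over a = 0 to k.

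- Perfect test: 0% under either denominator.
- Abbott, true negatives (q = 0.004, k = 10): 3.54%; × 0.90 = 3.2% of all participants (2.5% with attrition). Over those ever positive: 3.19 / 13.54 = 23.5%.
- Genetico, true positives (q = 0.96, k = 10): 30.6%; × 0.10 = 3.1% of all participants (2.4% with attrition).
- Either assay with fully persistent errors: 0%.

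**Dilution.** The ratio of the two denominators is 1 / 0.1354 = 7.4 for Abbott with independent errors and 1 / 0.10 = 10 for Genetico or a perfect test. The tie to prevalence shows in the Genetico figures: the same 30.6% of true positives reads 3.1% of participants at 10% prevalence and 6.1% at 20%.

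**The case against.** The strongest reply is that this is mainly a matter of labels. The definition says openly that one positive test is enough; cumulative ever-seropositivity is an interpretable quantity; new infection among those negative at entry is already covered by the incidence item; and either denominator can be computed from the same serial results. The measures are descriptive, and the main analyses in Section 5.3.1 are prevalence and its comparison over time. This stands as an argument about weight. It does not rescue the definition, because the protocol presents the quantity as seroconversion under an immune-dynamics objective.

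A second reply is that the 13.5% is one corner: Abbott only, 10 tests for everyone, independent errors. That is fair, hence the range of 10.4% to 13.5%. The 10% with a perfect test needs no assumption about test error.

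Three stronger readings are tempting and are not supported:

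- A reader might infer that dividing by all participants pushes seroreversion away from zero. It does the reverse. With a perfect test it is 0% either way; with Abbott and independent errors it is 3.2% over all participants against 23.5% over those ever positive. Test error creates the false reversions and the wide denominator hides them.
- A reader might infer that incidence is dominated by baseline prevalence. Section 5.3.2 excludes those positive at the first test from that calculation.
- A reader might infer that one positive result counts as a new case for incidence. The protocol does not define a new case, and an analysis plan may do so. If one Abbott positive were enough and errors were independent, the false rate would be 0.4% per 4-week interval, but that is conditional and does not describe a stated rule.

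**Conclusion.** The concern holds in limited form. Cumulative seroconversion as defined is ever-seropositivity and does not match the incidence item beside it. With no new infection it reads 10% at the planning prevalence with a perfect test, and 10.4% to 13.5% with Abbott over 10 tests (12.8% for independent errors with planned attrition). Cumulative seroreversion, on its literal wording, is diluted about 7- to 10-fold and moves with prevalence; a separate 0% to about 3% of participants can come from unconfirmed test errors.

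The error-related figures rest on the manufacturers' stated accuracy and on where the truth lies between persistent and independent errors. The inclusion of baseline positives and the denominator fault rest on the wording alone. This is a secondary objective: it should be corrected before analysis, but the main prevalence results do not depend on it.

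**What to change.** 1. **Seroconversion.** Restrict it to participants negative at the first test, and report the present quantity as cumulative ever-seropositivity. Restriction alone leaves up to 3.5% false converters with Abbott, so the main version should also require support for the first positive, from the second assay in the same serum or the next 4-weekly sample.
2. **Seroreversion.** Divide by participants with a prior positive. Use as the main analysis those whose first positive is supported by the second assay in the same serum. Judge later negatives on one assay named in advance, preferably repeated at the next sample. Changing the denominator without confirmation would expose the 23.5% above. A both-assay rule at every visit should be avoided: with 96% sensitivity and independent errors, 30.6% of true positives would show a false reversion over 10 tests. Repeating the negative matters most if the named assay is Genetico: for a true positive detected at the first visit, the chance of two consecutive false negatives in the nine later tests is at most 8 × 0.04² = 1.3%.
3. **Sensitivity analyses.** Report the single-result versions of both measures, and give a specificity-corrected or confirmed-case incidence alongside the main one.

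The cost is definition wording and a few lines of code, with no new visits; both assays are already planned. There are two small downsides. Genetico's 96% sensitivity would leave about 4 of 100 true baseline positives unsupported (1000 × 0.10 × 0.04). Results first seen at a participant's last visit cannot be confirmed by a later sample.

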**Table. Calculation of the study sample taking into account approximately 5% attrition at each visit**

	First visit	Week 4	Week 8	Week 12	Week 16	Week 20	Week 24	Week 28	Week 32	Week 36
Telephone-based questionnaire; medical hypothesis; IgG tests	1000	950	902	857	815	774	735	698	663	630

Study participants will be asked to undergo multiple tests for SARS-CoV-2 antibodies with 4-week intervals to assess the immune response dynamics. If a participant agrees to repetitive tests, they will also complete questionnaires with the objective of collecting epidemiological information for the period since the first test. Time of each round of survey and information collection will not exceed 4 weeks.

If the test is not performed in the mentioned interval, delayed testing data may be used. If before the initial or a later test a participant shows signs of acute respiratory infection (see Section 3.2.2.3) or has been diagnosed with COVID-19, the study will use results of

a test performed at least 2 days after all symptoms resolved, or results of the last negative test for the virus.

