### 5.3.1. Primary objective

**Cross-sectional study:** the main objective of this study is to calculate the proportion of participants with the presence of antibodies (taking into account the threshold recommended by manufacturer) in the total number of tested. Crude value will be equal to the proportion of positive-tested persons in the total number of enrolled. Additionally, standardized values and values in age or gender groups will be calculated as well as an adjusted value based on the total population in a region.

**Cohort study:** the main objective of the cohort study is to compare correspondent values of prevalence in different points in time. This comparison will be made using simple tests and models depending on the type of value (rough, standardized, adjusted).

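### Seroreversion is scored on one unconfirmed negative, and immune dynamics are summarised only as positive or negative although IgG titre is measured at up to 10 visits

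*Protocol*

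**What the plan says.** Protocol Section 2.2 lists the objective as "To evaluate individual immune dynamics (seroconversion, seroreversion"), so the term is explained by two threshold events. Section 3.1 plans repeated sampling: "It is planned to perform up to 10 visits which will include blood sampling, testing, and collection of additional information". Under the sample table in the same section the purpose is given: "Study participants will be asked to undergo multiple tests for SARS-CoV-2 antibodies with 4-week intervals to assess the immune response dynamics". Section 4 names the Abbott assay and says it is used "To measure IgG antibodies titer"; a Genetico total-Ig assay is run as well.

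Section 5.3.2 (cohort study) then fixes three measures. The first is "cumulative seropositivity, i.e. proportion of positive tests at each moment". The second is the cumulative share with one or more positives. The third, seroreversion, is the "cumulative proportion of participants at all moments with at least 1 negative test after at least 1 positive test".

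The cut-off is stated only for the cross-sectional analysis in Section 5.3.1 ("taking into account the threshold recommended by manufacturer"). I assume that it carries over to the cohort measures. Section 5.3.2 does not say which assay feeds them, and it sets no borderline zone, confirmatory result or minimum fall.

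**The concern.** There are two separate weaknesses.

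1. **Information measured but not used.** Up to 10 titres per person are reduced to a string of positives and negatives. A large fall that ends above the cut-off looks the same as no change.
2. **A fragile event definition.** One positive and one later negative make a seroreverter. Because the measure is cumulative, every further visit gives another chance of a discordant result, and an event once scored is never removed.

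At stake is the seroreversion figure. Section 6 promises public data for epidemic modelling, so a figure inflated by test error could be reused by others. The prevalence estimates are not affected.

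**Working it through.** **Inputs from the protocol.** Abbott sensitivity 100%, specificity 99.6%; Genetico sensitivity 96%, specificity 100% (Section 4, manufacturers' figures). Tested at successive visits: 1000, 950, 902, 857, 815, 774, 735, 698, 663, 630 (Section 3.1 table). Prevalence 10% (Section 5.1).

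**Assumptions.** Errors are independent between visits, each person's true status is constant, loss to follow-up is unrelated to test results, and no visit is missed before dropout.

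**Plan's own figure.** 1000 × 0.95^9 = 630.2, which matches the 630 stated for Week 36.

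**Formula.** With k tests, each positive with probability p, a person escapes being scored only if the results are a run of negatives (possibly none) followed by a run of positives (possibly none). So

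R(k, p) = 1 − Σ (1−p)^(k−j) p^j, summed over j = 0 to k.

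**All 10 visits attended.**
- Abbott, never infected, p = 0.004: 0.996^10 + 0.996^9 × 0.004 + smaller terms = 0.96071 + 0.00386 + 0.00002 = 0.96459, so R = 3.5%.
- Genetico, stably positive, p = 0.96: 0.96^10 + 0.96^9 × 0.04 + 0.96^8 × 0.04^2 + smaller terms = 0.66483 + 0.02770 + 0.00115 + 0.00005 = 0.69373, so R = 30.6%.

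**With attrition.** From the table, 50, 48, 45, 42, 41, 39, 37, 35 and 33 people stop after visits 1 to 9, and 630 complete visit 10. Weighting R(k, p) by these counts:
- Abbott: 0.9 × 630 × 0.0354 = 20.1 from completers, plus 4.8 from those who stop earlier, gives **24.9 of 900** never infected.
- Genetico: 0.1 × 630 × 0.3063 = 19.3 from completers, plus 4.9, gives **24.2 of 100** stable positives.

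| Prevalence | Abbott: never infected scored as reverted | Genetico: stable positives scored as reverted |
|---|---|---|
| 5% | 26 of 950 | 12 of 50 |
| 10% | 25 of 900 | 24 of 100 |
| 20% | 22 of 800 | 48 of 200 |

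**Confirmed rule** (two consecutive positives, later two consecutive negatives), same assumptions. With 10 visits: Abbott about 0.01%, Genetico about 1.1%. Weighted by the visit table: about 0.07 of 900 and about 0.8 of 100.

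**Waning above the cut-off** (illustration; half-life, starting level and an assay CV of 10% are assumed, and lognormal error was simulated at 4-week visits):
- Start at 8 times the cut-off, half-life 18 weeks: 8 × 2^(−36/18) = 2 times at Week 36, a 75% loss. Scored as seroreversion in about 0%; a per-person log-titre slope detects the fall in about 100%.
- Start at 4 times, half-life 26 weeks: 4 × 2^(−36/26) = 1.53 times, a 62% loss. Again about 0% against about 100%.
- Start at 2 times, half-life 18 weeks: 0.5 times at Week 36. The one-negative rule captures this in about 100%.

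**Noise near the cut-off** (CV assumed, no true change, 10 visits). Share scored as reverted under the one-negative rule:

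| Level relative to cut-off | CV 5% | CV 10% | CV 20% |
|---|---|---|---|
| 1.1 times | 23% | 80% | 96% |
| 1.25 times | 0% | 11% | 71% |
| 2 times | 0% | 0% | 0.2% |

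At 1.1 times and CV 10% the confirmed rule lowers 80% to 15%.

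**The case against.** The strongest reply is that the objective itself is threshold-based. Section 2.2 explains individual immune dynamics as seroconversion and seroreversion, and Section 5.3.2 measures exactly those. This stands. A reader might infer that the protocol asks how fast antibodies change in an individual and then fails to answer. It does not: no section asks for a rate, slope or half-life, so nothing is contradicted, and a titre model is an addition.

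A reader might also infer that the seroreversion figure would mainly reflect starting level and noise near the cut-off. The protocol does not support that either. It gives no assay CV, half-life or titre distribution, and no share of participants close to the cut-off. The noise is negligible at about 2 times the cut-off, and waning that clearly crosses the cut-off is captured.

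Third, Section 5.3 says in general terms that methods follow the type of variable, and a separate analysis plan or the results form (Appendix 3, not shown) may already provide for the numerical reading. This is fair for the titre model. It does not reach the seroreversion definition, which the protocol itself fixes.

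Fourth, Abbott's stated 100% sensitivity implies no false seroreversion among true positives; its false events come only from false positives that later test negative. That is correct. If cross-reactivity persists in the same people, those false positives would tend to stay positive and the count of 25 would fall.

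**Conclusion.** The point holds in limited form. The binary measures fit the objective as worded, but the seroreversion rule is fragile and the measured titre is left out of the dynamics analysis. On the protocol's own figures, false seroreversion could reach about 25 people on Abbott, set beside only about 100 truly positive at 10% prevalence, or about 24 of 100 stable positives on Genetico. Both counts rest on independent errors, constant true status and the manufacturers' accuracy figures. The Abbott count is an upper figure if cross-reactivity persists. Since Section 5.3.2 names no assay, either figure could apply.

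Waning that ends above the cut-off is invisible whatever values are assumed; how common it is cannot be judged from the document. The same is true of noise near the cut-off. This concerns one secondary objective of a descriptive study, and the change is worth making because it uses samples already planned.

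**What to change.** In Section 5.3.2:

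1. Keep the three binary measures and name the assay that feeds them.
2. Count seroreversion only when confirmed: two consecutive positives followed by two consecutive negatives, all on that same assay. Report the one-negative rule as a sensitivity analysis.
3. Add, as a supplementary analysis of the same objective, a mixed model of the log Abbott reading over time in participants with at least one positive, with participant-level intercept and slope. Allow for an early rise before decline, since a single straight line would mix the two.

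A minimum fall of 20% is a weaker substitute for confirmation. At 1.1 times the cut-off and an assumed CV of 10%, it would still label 62% of stable people as reverted if measured from the highest earlier positive, or 29% if measured from the first.

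Cost: export of the numerical reading with each result, one extra model, and fewer events labelled seroreversion. A reversion first seen at a participant's last visit cannot be confirmed, so some true late events move to the sensitivity analysis. No extra samples or visits are needed.

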## 6. Publication of the results

Results of this study will be published in forms of press-releases, preprints, and peer-reviewed scientific publications in Russian and English. Anonymized data will be publicly available for use in mathematical models of the epidemic dynamics and for the exchange of scientific information.

## CATI: Study of the spread of COVID-19 in St Petersburg, Russia

Good afternoon! My name is \_\_\_\_\_. The European University at St. Petersburg together with Scandinavia clinics perform a study of coronavirus spread in St. Petersburg residents. It is a very important study which will help to make decisions on the duration of self-isolation, and it gives residents an opportunity of a free-of-charge test to discover if you have already had the infection, as it may be asymptomatic.

Please answer several questions of this survey; it will take about 10 minutes.

a) At the end of this survey, if you are interested in this testing, I will explain in which clinics you can do it and ask your contact information, for the reception contacting you and giving you an appointment at time which suits you.

b) At the end of this survey, if you are interested in this testing, I will explain in which clinics you can do it and ask your contact information, for the reception contacting you and giving you an appointment at time which suits you. In this study, the testing is free-of-charge, and the commuting to the clinic will be also covered: you will receive a personal promocode for a taxi.

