## 5.2. Encouragement design

Even if random sample of potential participants (surveyed persons) is representative, the decision about the participation in the study may bias its results, as it is made (or rejected) by a potential participant. The assumption of ideal participation of all surveyed persons in the testing is unrealistic. The next step would be to assume self-selection based on the observed characteristics of the surveyed. But it is doubtful that during a telephonic interview all observed individual characteristics which may affect the decision about the participation may be identified and quantified. For this reason, the final assessment of the prevalence will be biased. To surpass the issue of non-observable decision about the voluntary participation, the encouragement design will be used in this study.

A randomly selected subgroup of the surveyed will be offered a benefit related to the study participation, free-of-charge taxi to the place of testing. This offer will be made during the interview. Such randomization will permit to assess the proportion of infected in the group of people whose decision to participate in the testing changes depending to this benefit. The prevalence assessed in this manner has higher external validity than the prevalence in the group of people who make the decision without external encouragement.

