### CLARIFICATIONS FOR AN INTERVIEWER:

What does the test show: it's a test for antibodies. It shows if you have had a coronavirus infection earlier (as this infection is often asymptomatic or similar to other diseases). It does not show if you are currently infected. It is free of charge.

Results of the test will not be reported to state organizations.

What are Scandinavia clinics: it's the largest private clinics chain in St. Petersburg, one of the centers of urgent medical care in case of coronavirus infection.

Q1001 Single choice from 'Q1001 list'

We guarantee that your answers will be kept confidential. For the quality control of my work, this call will be recorded, and the record will be deleted after the end of the study. Do you agree to proceed to a survey?

How can I refer to you?

informationText('Respondent name: ' + Q.openValueTxt);

Q1

Sex

(DON'T READ THE QUESTION, REGISTER THE ANSWER BASED ON EARLIER ANSWERS)

Single choice from 'Q1 list'

1 Male

2 Female

Q2

Please tell me, do you live in St. Petersburg?

(DON'T READ ANSWERS)

(A SINGLE ANSWER) Single choice from 'Q2 list'

1 Yes

2 No

If Q2=2, terminate the interview

Q3 Single choice from 'Q3 list'

In which district of St. Petersburg do you live?

(DON'T READ ANSWERS)

(A SINGLE ANSWER)

1 admiraltEiskiy

2 vasileostrOvskiy

3	vYborgskiy	
4	kAlininskiy	
5	kIrovskiy	
6	kOlpskiy	
7	krasnogvardEiskiy	
8	Krasnoselskiy	
9	KronshtAdtskiy (KronshtAdt)	
10	Kurortniy	
11	Lomonosovskiy	
12	Moskovskiy	
13	Nevskiy	
14	PetrogrAdskiy	
15	PetrodvortsOviy	
16	primOrskiy	
17	pUshkinskiy	
18	frUnzenskiy	
19	Centralniy	
998	OTHER (explain)	OpenValueTxt

Q4     Numeric

How old are you in full years?

If Q4(ValueInt<18), terminate the interview

Q5     Single choice from 'Q5 list'

Please tell me if since the beginning of February, you have been to somewhere outside of St. Petersburg and Leningrad region?

(DON'T READ ANSWERS)

(A SINGLE ANSWER)

1       Yes

2       No

Q6     Single choice from 'Q6 list'

Q5=1

Have you traveled abroad since the beginning of February?

1       Yes

2       No

Q7     Single choice from 'Q7 list'

Among the people who you have met after the 1st of March, are there people who have traveled abroad in February or later?

(DON'T READ ANSWERS)

(A SINGLE ANSWER)

1       Yes

2       No

999            (DON'T READ) Not sure

Q8

Have you exited your home during the last week (7 days)?

(DON'T READ ANSWERS)

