2: 'Thank you for your answers. You are offered free testing for anti-coronavirus antibodies

3: 'Thank you for your answers. You are offered free testing for anti-coronavirus antibodies 4: 'Thank you for your answers. You are offered free testing for anti-coronavirus antibodies

};

Q.text = code in texts ? texts[code] : 'Code text not found' + code;

Thank you for your answers!

You are offered free testing for anti-coronavirus antibodies at a Scandinavia clinic; it will show if you have or have not had the infection (or have it now). This is needed to evaluate the prevalence of this infection in our city, even if some people have had in in asymptomatic form.

a) If you agree, give me please your contact phone number, first and patronymic names (no last name). In the next 5 days, clinic representatives will contact you to discuss a moment for testing which suits you. Do you agree?

b) If you agree, give me please your contact phone number, first and patronymic names (no last name). In the next 5 days, clinic representatives will contact you to discuss a moment for testing which suits you and to explain how you can call for a free taxi to go to the clinic as a participant of this study. Do you agree?

CLARIFICATIONS FOR AN INTERVIEWER:

Any questions related to the testing results waiting time, its medical characteristics etc. might be asked to a clinic representative when they contact the respondent.

- 1 Name and patronymic name: OpenValueTxt
- 2 Contact phone number: OpenValueNum
- 3 No, do not agree Blocking

# Appendix 2

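### Introduction b) of the phone script promises the randomised taxi before survey consent, so comparability of the two arms among the surveyed is no longer guaranteed

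*Protocol*

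**What the plan says.** Protocol Section 5.2 sets up the encouragement: "A randomly selected subgroup of the surveyed will be offered a benefit related to the study participation, free-of-charge taxi to the place of testing". On timing it adds: "This offer will be made during the interview". The stated purpose is to "assess the proportion of infected in the group of people whose decision to participate in the testing changes depending to this benefit". The decision to be shifted is the one about testing, not the one about answering the survey.

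Appendix 1 holds the telephone script. The introduction has two versions. Both contain the line "At the end of this survey, if you are interested in this testing, I will explain in which clinics you can do it". Only version b) goes on to say that "the commuting to the clinic will be also covered: you will receive a personal promocode for a taxi". The consent item, Q1001, follows: "Do you agree to proceed to a survey". Questions Q1 to Q35 come after that. The closing text at Q36 again has two versions, and version b) says the clinic will call "to explain how you can call for a free taxi to go to the clinic as a participant of this study".

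Section 5.3 lists five outputs. One is a prevalence corrected for self-selection on unobserved characteristics. Section 5.3.1 defines the main cross-sectional result as the proportion antibody-positive, with standardised and adjusted values.

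**The concern.** An encouragement works as an instrument because chance alone decides who gets it within the group analysed. Section 5.2 names that group as the surveyed. In the script, a person in the taxi arm hears of the taxi before deciding whether to be surveyed, and then answers every question knowing of it. Survey consent and survey completion are therefore decided after assignment and may depend on it. If the taxi brings in people who would otherwise have declined the survey, the surveyed in arm b) include a type of person missing from arm a).

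At stake is the tool that Section 5.2 introduces because observed characteristics are not expected to explain participation. The two quantities exposed are the prevalence among people whose testing decision the taxi changes, and the selection-model estimate when it is fitted to survey respondents.

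**Working it through.** **Order of events, side by side**

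| Step | Section 5.2 | Appendix 1, arm b) |
|---|---|---|
| Taxi first mentioned | within the interview, to some of the surveyed | introduction, before Q1001 |
| Survey consent | precedes the offer, if only the surveyed receive it | Q1001, after the taxi sentence |
| Covariates | – | Q1–Q35, after the taxi sentence |
| Taxi offered at the end | – | Q36 b) |

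Q36 b) already delivers the offer, so the early sentence is not needed for that purpose.

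**The plan's own figure.** No stated figure is in dispute. The 2-point planning error used below for scale reproduces: (1.96 × 0.5 / 0.02)² − 4 = 2397, and at 10% prevalence (1.96 × 0.3 / 0.02)² − 4 = 860, which is below 900.

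**Illustration; every input is assumed.** Per person surveyed without the taxi, 0.20 test and 12% of them are positive (0.024). The taxi converts a further 0.05 to testing, 6% positive (0.003). The early announcement also brings in e extra respondents, all of whom test, with prevalence pe.

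- Arm a): tested 0.20, positive 0.024.
- Arm b): tested (0.25 + e)/(1 + e), positive (0.027 + e·pe)/(1 + e).
- Ratio estimate = difference in positives / difference in tested. Multiplying both by (1 + e) gives [0.003 + e(pe − 0.024)] / [0.05 + 0.8e].
- Target, all testers induced by the taxi = (0.003 + e·pe)/(0.05 + e).

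| e | pe | Estimate | Target | Difference, points (relative) |
|---|---|---|---|---|
| 0.02 | 6% | 0.00372/0.066 = 5.64% | 6.00% | −0.36 (−6%) |
| 0.05 | 6% | 0.00480/0.090 = 5.33% | 6.00% | −0.67 (−11%) |
| 0.10 | 6% | 0.00660/0.130 = 5.08% | 6.00% | −0.92 (−15%) |
| 0.02 | 3% | 0.00312/0.066 = 4.73% | 5.14% | −0.42 (−8%) |
| 0.05 | 3% | 0.00330/0.090 = 3.67% | 4.50% | −0.83 (−19%) |
| 0.10 | 3% | 0.00360/0.130 = 2.77% | 4.00% | −1.23 (−31%) |

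**When the bias vanishes.** Write T for the target and M = 0.05 + e. The estimate is (TM − 0.024e)/(M − 0.20e). For e > 0 it equals T only if T = 0.024/0.20 = 12%. So the pooled prevalence of converted testers plus extras must equal that of people who test anyway. Extras at 12% are not enough: the estimates are 7.45%, 8.67% and 9.69% against 7.71%, 9.00% and 10.00%, a bias of about −3% to −4%. Extras would need (0.12M − 0.003)/e = 27%, 18% or 15%.

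**Second set of assumed inputs.** Keep the 20% who always test at 12%, set the converted 5 points at 10% positive, and let extra entry be 5%.

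- 80% of extras test, 5% positive: (0.005 + 0.002 − 0.0012)/(0.05 + 0.04 − 0.01) = 7.3%.
- 80% test, 15% positive: (0.005 + 0.006 − 0.0012)/0.08 = 12.3%.
- None test: (0.005 − 0.0012)/(0.05 − 0.01) = 9.5%.

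Against the 10.0% among converted testers who would have been surveyed anyway, the result can move either way. Much of that movement is a change of target: the pooled prevalence is 0.007/0.09 = 7.8% in the first case and 0.011/0.09 = 12.2% in the second.

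**Scale of sampling error.** Assume 1000 tested and equal arms. SE = √[(Va + Vb)/n] / (difference in tested), where V is the variance of tested × (result − estimate). For e = 0.02 and pe = 6%, n = 1000/(0.20 + 0.2647) = 2152 surveyed per arm, Va = 0.0218 and Vb = 0.0252. SE = √(0.0470/2152)/0.0647 = 7.2 points. The same formula at e = 0.10 gives about 4 points.

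**All randomised contacts.** With the same number called in each arm and no testing among people who refuse Q1001, the common denominator cancels. At e = 0.05 and pe = 6% the ratio is (0.003 + 0.003)/(0.05 + 0.05) = 6.0%, which is the target.

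**The case against.** The strongest reply is that nothing here shows harm. Both introductions already announce a free test, so the taxi may add little to the decision to answer a 10-minute survey. If consent does not respond to it, there is no bias. This stands: the protocol gives no consent figures by version.

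Second, Section 5.2 can be read to fit the script. It uses surveyed persons as a gloss for potential participants, and an offer during the interview could loosely include the introduction. That softens the contradiction but does not remove it. A person who refuses at Q1001 is not surveyed in the ordinary sense, and Section 5.2 speaks of characteristics learned in the interview.

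Third, the illustrated shifts of 0.4 to 1.2 points are below the 2-point planning error and well below the ratio's own standard error of about 4 to 7 points. The −31% comes from one corner: extras twice as numerous as the converted testers, all testing, at 3% prevalence. This also stands, although sampling error is no reason to keep an avoidable bias.

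Fourth, handling may partly exist. Q1001 is a coded item, and a stored code (Q8001) selects the closing text, so a check by version may be possible. The protocol does not show how that code is defined or whether it is kept for refusals. Such a check could be left to an analysis plan, but the script order cannot be: it is fixed in this appendix, and analysis cannot restore randomisation among the surveyed.

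A reader might infer that the taxi does change who is surveyed, that randomisation has failed, or that the study's prevalence is biased. The document supports none of these. Assignment may still be random among everyone called. The crude prevalence of Section 5.3.1 and the estimates adjusted for observed characteristics do not need the taxi as an instrument.

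**Conclusion.** The point holds as a weakness in design and a mismatch between Section 5.2 and Appendix 1. The script lets the randomised offer act on survey entry, so comparability of the arms among respondents is no longer protected by randomisation. If consent or completion differs by version, the prevalence among people moved by the taxi can be biased, and so can the estimate corrected for unobserved self-selection when fitted to respondents.

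The size is unknown. The first illustration gives −0.4 to −1.2 points, or −6% to −31%, against all testers induced by the taxi. The second shows that the direction depends on the assumptions and on which group is the target. The bias is zero only if survey entry does not depend on the offer, or if the taxi-induced testers, extras included, have the same prevalence as those who test anyway.

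This should be fixed. It is not critical, because it touches one of the five outputs in Section 5.3 and the complier prevalence of Section 5.2, not the crude result.

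**What to change.** Use introduction a) in both arms, delete the taxi sentence from introduction b), and make the offer only at Q36 b), after Q1–Q35. Section 5.2 and Appendix 1 then agree. The cost is a script edit; survey response in the taxi arm may be slightly lower.

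For calls already made with introduction b):

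- Keep the assigned version for every person called, including those who refuse at Q1001.
- Report Q1001 consent and survey completion by version.
- Compute the simple ratio estimate on all randomised contacts. It needs only assignment, testing and result.
- State that this does not repair the covariate-based selection model, because people who refuse at Q1001 have no covariates.

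The cost is one retained variable and a short table.
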